- Hemoglobin \geq 11.0 g/dL for African American subjects; Hemoglobin \geq 11.5 for non-African American subjects
- Normal screening labs (with exception of the expected hormonal abnormalities inherent in hyperandrogenemia)
- Sexually active subjects must agree to abstain or use double barrier contraception during the study
- Subjects must agree not to take any other medications during the course of the study without approval by the study investigators.

2. List the criteria for exclusion

- Abnormal screening labs (with the exception of the expected hormonal abnormalities inherent in hyperandrogenemia)
- Creatinine clearance less than 90 ml/min as calculated by Cockcroft-Gault equation
- Hemoglobin <11.5 g/dL for non-African American subjects; Hemoglobin < 11.0 g/dL for African American subjects
- Abnormal liver function tests (including AST, ALT, Bilirubin, Albumin, and Alkaline Phosphatase)
- Weight < 34 kg
- History of renal dysfunction, liver dysfunction, congestive heart failure, deep venous thrombosis, breast cancer, endometrial cancer, or cervical cancer
- Pregnant or breast feeding
- On medications known to affect the reproductive axis within 3 months of the study (including oral contraceptive pills, metformin, and spironolactone)
- Are currently participating in another study or have been in one in the last 30 days.
- Subjects using restricted medication (see restrictions below) are excluded unless the subject's primary care provider approves stopping the medication.

3. List any restrictions on use of other drugs or treatments.

Subjects must not take medications known to affect the reproductive axis (including oral contraceptives, metformin, and spironolactone) for 90 days prior to and during the study.

Subjects must not take medications that have the potential to increase metformin blood concentration (including cationic drugs such as amiloride, digoxin, morphine, procainamide, quinidine, quinine, ranitidine, triamterene, trimethoprim, vancomycin which are eliminated by renal tubular secretion have the potential for interaction with metformin by competing for common renal tubular transport systems; cimetidine, which increases (by 60%) peak metformin blood concentrations; furosemide which can increase metformin blood concentration without altering metformin renal clearance; and nifedipine, which can increase metformin absorption). Subjects should limit their intake of alcohol.

Statistical Considerations

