
Day 1: Begin Estradiol and Progesterone

Starting the day of discharge from the first inpatient admission, subjects will be given oral estrogen (estrace, 0.5-1 mg once a day) and oral progesterone suspension (20 mg/ml, 25-100 mg) three times a day at 0700, 1500, and 2300 hr for seven days. The first dose will be given at 1500 on the day of discharge. If the 1500 dose is incompatible with school schedules, alternative dosing schedules can be arranged. Generally this will entail taking the afternoon dose immediately upon returning home from school without any change in the morning and evening dosing times. Dosages will be based on weight. The target mean plasma progesterone concentration is 2-8 ng/dL. Each subject will be instructed to eat a small snack with the progesterone syrup as it has been observed that the absorption of progesterone is influenced by the presence or absence of food.

Subjects will also be given oral iron supplementation at a dose of 1-2 mg/kg. Subjects will be given iron tablets (which contains 27 - 65 mg elemental iron) with proper dose instructions. Subjects weighing ≤ 36 kg will be given 1 tablet a day and subjects weighing >36 kg will be given 2 tablets a day to be taken for the duration of the study.

Day 3 and Day 5: Outpatient blood draws

On study days 3 subjects will have blood drawn at 1700 hr (two hours after the 1500 hr progesterone dose to check serum estrogen, peak progesterone levels, and hemoglobin. On study day 5, subjects will have blood

IRB-HSR# 13789: Effect of Metformin on Sensitivity of the GnRH Pulse Generator to Suppression by Estradiol and Progesterone in Hyperandrogenic Adolescent Girls

drawn at 1700 hr (two hours after the 1500 hr progesterone dose) to check serum estrogen and peak progesterone levels.

Day 7: Second inpatient admission

The second inpatient admission will begin on day 7. The procedure will be identical to the first inpatient admission until 07:00 hr. An OGTT will not be done during this admission; however, a fasting glucose and insulin will be drawn at this time and then the admission will end at 07:00 hr. Subjects will be required to bring any unused estrogen and progesterone (or the empty bottles) to the admission. Subjects will discontinue the estradiol and progesterone after the completion of the second inpatient admission, but will continue taking iron supplementation. At the time of discharge, subjects will be given Metformin.

Day 8: Begin Metformin

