NOTE: Risk of unplanned pregnancy: If a research subject is sexually active and stops using hormonal contraception while failing to use another non-hormonal method of contraception, there is a risk of unplanned pregnancy. (However, subjects will be counseled to use non-hormonal methods of contraception if sexually active.)

NOTE regarding the risk associated with EMLA cream (topical lidocaine and prilocaine, used to alleviate pain): The risks of lidocaine and prilocaine in general may include (frequency not defined) hypotension, angioedema, shock, hyperpigmentation, erythema, itching, rash, burning, urticaria, burning, stinging, edema, bronchospasm, and hypersensitivity reactions. However, in the case of topical lidocaine/prilocaine use, the non-dermatologic adverse events mentioned above would be extremely unlikely unless large amounts of topical lidocaine/prilocaine were used (allowing significant systemic absorption).

2.2 List by bullet format a summary of safety tests/procedures/observations to be performed.

- Sterile technique will be used.
- Before participation in the studies, all participants will be required to have a normal hemoglobin (≥ 11.5 g/dL for non-African American subjects and ≥ 11.0 g/dL for African American subjects). Hemoglobin levels will be measured prior to every admission. For African American subjects, if the hemoglobin level is < 11.0 , the study will be discontinued. For non-African American subjects, if the hemoglobin level is < 11.5 g/dl, the study will be discontinued.
- Blood loss will be carefully recorded and limited to a maximum of 7cc/kg (10% of estimated total blood volume) in 8 weeks. A total of 467 ml of blood will be drawn during the study (including estimated waste from frequent blood draws), with no more than 243.5 being drawn during any 8 week period. Therefore, girls weighing less than 35 kg will not be able to participate. Iron supplementation (325 mg once or twice a day dependent on weight) will be prescribed to all participants.
- We will warn participants against becoming pregnant during the study. We will require that sexually active subjects use effective double barrier methods of birth control as needed during the study. β -hCG levels will be measured at screening and prior to each admission; if the β -hCG is positive, the study will be discontinued.

2.3 Under what criteria would an INDIVIDUAL SUBJECT'S study treatment or study participation be stopped or modified

At subject, PI or sponsor's request

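### The exclusion list sets the minimum weight at 34 kg, but the safety plan's blood-loss cap requires 35 kg; at 34 kg the planned draw can exceed the cap by up to 5.5 mL

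*Combined protocol and SAP*

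**What the plan says.** Two places in the current text set a minimum weight.

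- **Inclusion/Exclusion Criteria, item 2 (exclusion list).** The criterion reads "Weight < 34 kg - History of renal dysfunction, liver dysfunction, congestive heart failure"; the words after the dash belong to the next bullet. No reason is given for 34 kg.
- **Data and Safety Monitoring Plan, item 2.2.** The rule on volume is "Blood loss will be carefully recorded and limited to a maximum of 7cc/kg (10% of estimated total blood volume) in 8 weeks". The planned volume over the whole study is put at 467 mL, waste included. For the 8-week window that the cap refers to, the plan is stated as "with no more than 243.5 being drawn during any 8 week period". The consequence drawn is "Therefore, girls weighing less than 35 kg will not be able to participate".

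Both are operative protocol text, and neither refers to the other.

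**The concern.** A girl who weighs at least 34 kg but less than 35 kg passes the exclusion list and fails item 2.2. Both statements decide who may enter, so one of them must be wrong, and only item 2.2 shows where its number comes from.

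The exclusion list is where staff would naturally check eligibility, and it carries the less protective number. If it is used alone, a girl can be enrolled whose planned maximum draw is above the limit the protocol sets for her. Staff must then either stop sampling short of plan to respect the cap or exceed it. Her enrolment also complies with one section and departs from another. The participants are minors, and the protocol equates the cap with 10% of estimated total blood volume, so the threshold should be unambiguous.

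**Working it through.** **Inputs**

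- Cap on blood loss: 7 mL/kg in 8 weeks (item 2.2).
- Planned maximum in any 8 weeks: 243.5 mL (item 2.2).
- Minimum weight in the safety plan: 35 kg (item 2.2).
- Minimum weight in the exclusion list: 34 kg (Inclusion/Exclusion Criteria, item 2).

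The 467 mL total covers the whole study and does not enter the 8-week calculation.

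**Step 1: reproduce the safety plan's figure.** Minimum weight = planned maximum / cap per kg = 243.5 / 7 = 34.79 kg. Rounded up to a whole kilogram this is 35 kg, as item 2.2 states.

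**Step 2: test each threshold against the cap.** Allowed volume = 7 × weight. Excess = 243.5 − 7 × weight.

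| Weight (kg) | Allowed (mL) | Planned maximum (mL) | Excess (mL) | Planned maximum per kg (cc/kg) |
|---|---|---|---|---|
| 34.0 | 238.0 | 243.5 | 5.5 over | 243.5/34 = 7.16 |
| 34.5 | 241.5 | 243.5 | 2.0 over | 243.5/34.5 = 7.06 |
| 35.0 | 245.0 | 243.5 | 1.5 within | 243.5/35 = 6.96 |

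Relative excess at 34.0 kg: 5.5 / 238.0 = 2.3%.

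**Step 3: find the affected band.** At 34.78 kg the cap is 7 × 34.78 = 243.46 mL, just below 243.5. At 34.79 kg it is 7 × 34.79 = 243.53 mL, just above. Girls from 34.0 kg to just under 34.79 kg are therefore eligible under the exclusion list with a planned maximum over the cap. The band is about 34.79 − 34.0 = 0.79 kg wide. Girls from 34.79 kg up to but not including 35 kg are within the cap, but item 2.2 bars them because its limit is rounded up.

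**The case against.** The case for leaving this alone has several parts.

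- **The stricter rule is already written.** The two limits can be met together, since any girl of 35 kg or more satisfies both. Item 2.2 also applies the 7 cc/kg cap to everyone, so a girl of 34 kg enrolled in error should have her draws stopped at 238 mL. This stands, and it means the 5.5 mL excess arises only if the exclusion list is applied without item 2.2 and the full ceiling is drawn. It does not remove the conflict over who is eligible.
- **Few or no girls will be in the band.** The Background gives mean BMIs of 33 and 34 kg/m² for subgroups in the team's related study. At a BMI of 33, a weight of 34.79 kg implies a height of √(34.79/33), about 1.03 m, which is implausible for most girls in the age range. That is a different study, however, and this protocol sets no BMI minimum, so a lean 10-year-old could fall in the band.
- **Other safeguards apply.** Hemoglobin is measured before every admission, and a low value ends participation. That helps, but it does not measure cumulative volume, and the individual stopping criteria in item 2.3 do not list the volume cap.
- **The purpose of the 34 kg figure is not stated.** Tying it to the blood-loss cap is an inference. Whatever its purpose, it remains the lower of two limits and fails the cap.

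The separate iron dose under Day 1 ("Subjects weighing ≤ 36 kg will be given 1 tablet a day") shows that the protocol provides for girls near this weight. It fits a 35 kg minimum equally well, so it is no evidence that girls of 34.0 to 34.79 kg were expected.

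**Conclusion.** The concern holds. The safety plan's 35 kg is correct on its own inputs, and the exclusion list's 34 kg is inconsistent with it and with the blood-loss cap. The error is an inconsistent eligibility threshold; the calculation in item 2.2 is sound.

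The worst case is 5.5 mL, or 2.3% over the cap, for a girl of exactly 34 kg from whom the full 243.5 mL is drawn in 8 weeks. This takes the 243.5 mL ceiling and the 7 mL/kg cap as stated. The documents do not say how many girls might be in the band; few of the 60 are likely to be. This is a minor correction to safety and eligibility text, worth making because it concerns a blood-volume limit in minors. No effect on sample size, power or the primary contrast has been shown.

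**What to change.** In Inclusion/Exclusion Criteria, item 2, change the weight criterion to **Weight < 35 kg**. Every eligible girl's planned maximum would then be within the cap, with 245.0 − 243.5 = 1.5 mL to spare at the threshold, and both sections would give the same limit.

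The cost is one number. The change removes from the exclusion list's eligible range a band of less than 1 kg that item 2.2 already bars. It does keep out girls from 34.79 kg to just under 35 kg who would meet the cap; that follows from the rounding already in item 2.2 and is a reasonable price for a whole-number threshold.

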2.5 What are the criteria for breaking the blind/mask?

NA – Not blinded/masked

2.6 How will subject withdrawals/dropouts be reported to the IRB prior to study completion?

IRB-HSR continuation status form

3. Adverse Event / Unanticipated Problem Recording and Reporting

3.1 Will all adverse events, as defined in section 1.1, be collected/recorded? Yes.

3.2 How will adverse event data be collected/recorded?

Paper AE forms/source documents

Spreadsheet (*paper or electronic*)

3.3. How will AEs be classified/graded?

Mild/Moderate/Severe

Serious/Not serious

3.4 What scale will the PI use when evaluating the relatedness of adverse events to the study participation?

The PI will determine the relationship of adverse events to the study using the following scale:

Related:	AE is clearly related to the intervention
Possibly related:	AE may be related to the intervention
Unrelated:	AE is clearly not related to intervention

3.5 When will recording/reporting of adverse events/unanticipated problems begin?

After subject begins study drug/ device placement/intervention /study-related procedure/specimen collection

3.6 When will the recording/reporting of adverse events/unanticipated problems end?

End of study drug/device/intervention/participation

IRB-HSR# 13789: Effect of Metformin on Sensitivity of the GnRH Pulse Generator to Suppression by Estradiol and Progesterone in Hyperandrogenic Adolescent Girls

 X 30 days post study drug

3.7 How will Adverse Events, Unanticipated Problems, Protocol Violations and Data Breaches be reported? Complete the table below to answer this question

Type of Event	To whom will it be reported:	Time Frame for Reporting	How reported?
Any internal event resulting in death that is deemed DEFINITELY related to (caused by) study participation An internal event is one that occurs in a subject enrolled in a UVa protocol	IRB-HSR	Within 24 hours	IRB Online and phone call www.irb.virginia.edu/
Internal, Serious, Unexpected adverse event	IRB-HSR	Within 7 calendar days from the time the study team received knowledge of the event. Timeline includes submission of signed hardcopy of AE form.	IRB Online www.irb.virginia.edu/
Unanticipated Problems that are not adverse events or protocol violations This would include a Data Breach.	IRB-HSR	Within 7 calendar days from the time the study team received knowledge of the event.	Unanticipated Problem report form. http://www.virginia.edu/vprgs/irb/HSR_docs/Forms/Reporting_Requirements-Unanticipated_Problems.doc)
Protocol Violations (The IRB-HSR only requires that MAJOR violation be reported, unless otherwise required by your sponsor, if applicable.) Or Enrollment Exceptions	IRB-HSR	Within 7 calendar days from the time the study team received knowledge of the event.	Protocol Violation and Enrollment Exception Reporting Form http://www.virginia.edu/vprgs/irb/hsr_forms.html Go to 3rd bullet from the bottom.

IRB-HSR# 13789: Effect of Metformin on Sensitivity of the GnRH Pulse Generator to Suppression by Estradiol and Progesterone in Hyperandrogenic Adolescent Girls

Data Breach	The UVa Corporate Compliance and Privacy Office, a	As soon as possible and no later than 24 hours from the time the incident is identified.	UVa Corporate Compliance and Privacy Office- [contact]
	ITC: if breach involves electronic data-	As soon as possible and no later than 24 hours from the time the incident is identified.	ITC: Information Security Incident Reporting procedure, http://www.itc.virginia.edu/security/reporting.html
	UVa Police if breach includes such things as stolen computers.	IMMEDIATELY.	Phone- [contact]

UVa PI Held IND/IDE			
Life-threatening and/or fatal unexpected events related or possibly related to the use of the investigational agent.	FDA	Within 7 calendar days of the study team learning of the event	Form FDA 3500A (MedWatch) or narrative
Serious, unexpected and related or possibly related adverse events	FDA	Within 15 calendar days after the study team receives knowledge of the event	Form FDA 3500A (MedWatch) or narrative
All adverse events	FDA	Annually	IND annual report

4. How will the endpoint data be collected/recorded.

Database: *specify*

5. Data and Safety Oversight Responsibility

5.1. Who is responsible for overseeing safety data for this study ?

No additional oversight body other than PI at UVa (*skip question 5.2*)

5.2. What is the composition of the reviewing body and how is it affiliated with the sponsor? N/A

5.3. What items will be included in the aggregate review conducted by the PI?

All adverse events

Unanticipated Problems

Protocol violations

Audit results

Application of dose finding escalation/de-escalation rules *These should be outlined under 2.4.*

Application of study designed stopping/decision rules

IRB-HSR# 13789: **Effect of Metformin on Sensitivity of the GnRH Pulse Generator to Suppression by Estradiol and Progesterone in Hyperandrogenic Adolescent Girls**

Early withdrawals

Whether the study accrual pattern warrants continuation/action

Endpoint data

5.4 How often will aggregate review occur?

For additional information on aggregate review see:

www.virginia.edu/vpr/irb/hsr/continuations.html#aggreview

Annually

5.5. How often will a report, regarding the outcome of the review by the DSMB/DSMC, be sent to the UVa PI?

A copy of these reports must be sent to the IRB if applicable as soon as they are received by the PI. Do not wait until the next continuation to submit them to the IRB.

NA- there is no DSMB/ DSMC overseeing this study

5.6. How will a report of the information discussed in question 5.4 OR 5.5 be submitted to the IRB?

Part of IRB-HSR continuation status form

Payment

1. Are subjects being reimbursed for travel expenses (receipts /mileage required)? No.

2. Are subjects compensated for being in this study? Yes.

2a. What is the maximum TOTAL compensation to be given over the duration of the protocol?
\$400

2b. Explain compensation to be given.

All participants will receive a \$75 Simon Mall gift card per inpatient admission. In addition, participants will receive a \$100 bonus, also in the form of a gift card, for completing the medication regimen and outpatient blood draws. Therefore, a participant who completes the entire study will receive a total of \$400 in gift cards. This payment will not be provided to the subject until the end of study participation at the last overnight admission. If a subject withdraws from the study before it is complete, she will receive a \$75 gift card for each overnight admission she has completed.

2c. Is payment pro-rated (e.g. some compensation is given even if subjects do not complete the entire study)?

Yes. See explanation above.

If No, explain why payment cannot be pro-rated.

2d. Is money paid from UVa or State funds (including grant funds) or will items such as gift cards be distributed through UVa? Yes.

2d(i). How will the researcher compensate the subjects?

Gift cards

2d(ii). Which category/ categories best describes the process of compensation?

Compensation will include an alternative method (petty cash, gift card, other) and tax information will be collected, securely stored, and submitted electronically to Procurement Services as required.

► If an alternate method will be used justify why you are unable to issue checks through the UVa Oracle or state system.

This study involves adolescent girls. In past and on-going studies involving the same patient population, we have found that the girls prefer being given gift cards directly at the end of the study to receiving a check in the mail 4-6 weeks later, and this preference is reflected in our ability to recruit subjects. Therefore, we prefer to compensate the adolescent subjects with gift cards. We obtain social security numbers for IRS purposes.

IMPORTANT: If you check this box you will be required to submit the subjects' name, Social Security number, full address and amount of payment to Procurement at the end of each calendar year. The Office of the VP for Research will send you instructions on this procedure at a later date.

Risk/ Benefit Analysis

1. What are the potential benefits for the participant as well as benefits which may accrue to society in general, as a result of this study?

The goal of this study is to advance our knowledge of the effects of adolescent hyperandrogenemia and the mechanisms of development of polycystic ovary syndrome. Hopefully, this knowledge will lead to more effective means of preventing and treating PCOS in the future.

While treatment is not the goal of this study, it is possible that individual subjects may experience improvement in symptoms during the course of the study given that Metformin is commonly used in clinical practice to treat adolescent hyperandrogenemia and PCOS.

2. Analyze the risk-benefit ratio.

This study involves minimal risks and may provide valuable information about the development of polycystic ovary syndrome (PCOS). There are no long-term risks associated with blood sampling or the short term administration of physiologic doses of estradiol and progesterone. Metformin is associated with minimal risk in subjects with normal kidney, liver, and cardiac function, and subjects with such organ dysfunction will be excluded from the study. This study offers significant potential benefits to society as a whole and girls with hyperandrogenemia in particular. We hope that a better understanding of the effects of hyperandrogenemia in adolescent girls and the role of adolescent hyperandrogenemia in the development of PCOS will lead to improved prevention of the disorder as well as more effective treatments. In addition, some subjects may experience improvement in their hyperandrogenic symptoms while being treated with Metformin, as this

APPENDIX: Legal/Regulatory

Recruitment

The following procedures will be followed:

- *Finders fees will not be paid to an individual as they are not allowed by UVa Policy*
- *All recruitment materials will be approved by the IRB-HSR prior to use. They will be submitted to the IRB after the IRB-HSR has assigned an IRB-HSR # to the protocol.*

IRB-HSR# 13789: Effect of Metformin on Sensitivity of the GnRH Pulse Generator to Suppression by Estradiol and Progesterone in Hyperandrogenic Adolescent Girls

- *Only those individuals listed as personnel on this protocol will recruit and or conduct the consenting process with potential subjects.*

Retention Incentives

Any item used by the sponsor/ study team to provide incentive to a subject to remain in the study, other than compensation identified in the Payment section, will be submitted to the IRB for review prior to use. The IRB-HSR will provide the study team with a Receipt Acknowledgement for their records. Retention incentive items are such things as water bottles, small tote bags, birthday cards etc. Cash and gift cards are not allowed as retention incentives.

Clinical Privileges

The following procedures will be followed:

- *Investigators who are members of the clinical staff at the University of Virginia Medical Center must have the appropriate credentials and been granted clinical privileges to perform specific clinical procedures whether those procedures are experimental or standard.*
- *The IRB cannot grant clinical privileges.*
- *Performing procedures which are outside the scope of the clinical privileges that have been granted may result in denial of insurance coverage should claims of negligence or malpractice arise.*
- *Personnel on this protocol will have the appropriate credentials and clinical privileges in place before performing any procedures required by this protocol.*
- *Contact the Clinical Staff Office- [name] or [name] for further information.*

Sharing of Data/Specimens

Data and specimens collected under an IRB approved protocol are the property of the University of Virginia. You must have “permission” to share data/ specimens outside of UVa other than for a grant application and or publication. This “permission” may come in the form of a contract with the sponsor or a material transfer agreement (MTA) with others. A contract/ MTA is needed to share the data outside of UVa even if the data includes no HIPAA identifiers and no code that could link the data back to a HIPAA identifier.

- *No data will be shared outside of UVa, beyond using data for a grant application and or publication, without a signed contract/MTA approved by the SOM Grants and Contracts office/ OSP or written confirmation that one is not needed.*
- *No specimens will be shared outside of UVa without a signed contract/MTA approved by the SOM Grants and Contracts office/ OSP or written confirmation that one is not needed.*

Prisoners

If the original protocol/ IRB application stated that no prisoners would be enrolled in this study and subsequently a subject becomes a prisoner, the study team must notify the IRB immediately. The study team and IRB will need to determine if the subject will remain in the study. If the subject will remain in the study, the protocol will have to be re-reviewed with the input of a prisoner advocate. The prisoner advocate will also have to be involved in the review of future continuations, modifications or any other reporting such as protocol violations or adverse events.

Prisoner- Individuals are prisoners if they are in any kind of penal institution, such as a prison, jail, or juvenile offender facility, and their ability to leave the institution is restricted. Prisoners may be convicted felons, or may be untried persons who are detained pending judicial action, for example, arraignment or trial.

For additional information see the OHRP website at <http://www.hhs.gov/ohrp/policy/populations/index.html>

